The primary efficacy endpoint is the proportion of subjects surviving to 12 months of age. It is not anticipated that any subjects will be lost to follow-up prior to 12 months of age, but a subject who is not confirmed to have survived to 12 months of age will not be considered to have met the primary endpoint. As a complementary analysis, Kaplan-Meier survival curves of survival since birth and survival since first dose of IMP will be presented. Survival at 18 and 24 months of age will be analyzed as described for the primary endpoint. Median age at death will also be calculated. A Kaplan-Meier estimate of median survival past first dose of IMP will be computed. Estimated survival rates and median age at death derived from this study will be compared to rates/times reported in the literature, and will be discussed in conjunction with information derived from a natural history study in a similar patient population (study LAL-1-NH01).

Anthropometric indicators of growth, standardized by age and gender in accordance with the methodology described by the WHO and using WHO growth charts, will be listed by study time point as observed values and as changes from baseline. Change from baseline in anthropometric data will be tabulated as continuous data. In addition, the percentages of subjects who meet criteria for underweight, stunting, and wasting will be tabulated for each timepoint. For anthropometric indicators of growth, age will be adjusted for prematurity if gestational age is <37 weeks and the subject is under 12 months of age. The adjustment will be made such that corrected age equals the chronological age minus the number of months premature.

Change and/or percent changes from baseline in AST, ALT, and serum ferritin will be tabulated for each evaluation timepoint. The proportion of subjects with abnormal hemoglobin at baseline who achieve transfusion-free hemoglobin normalization (TFHN) will be summarized, as will the proportion of subjects who maintain transfusion-free normal hemoglobin.

The Denver II total score and functional area scores will be derived from the questionnaire in accordance with the Technical Manual and compared to appropriate demographic norms. The total score and functional area scores will be summarized as continuous data and according to the classification as to whether the subject displays abnormal/normal development.

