3.1.1.1 Dose escalation criteria during first 3 months of treatment

During this period, a subject may be considered for dose escalation if he/she meets 2 or more of the following criteria after at least 4 infusions at a dose of 1 mg/kg qw:

- Failure to gain an average of 5 g/kg body weight per day AND the presence of either of the following:
 - weight-for-length (WFL) or weight-for-height (WFH) z-score <-2 based on World Health Organization (WHO) child growth standards; and/or
 - length-for-age (LFA) or height-for-age (HFA) z-score <-2 based on WHO child growth standards.
- Albumin <3.5 g/dL;
- Alanine aminotransferase (ALT) >2x upper limit of normal (ULN);

Page 27 of 76

• Ongoing requirement for blood and/or platelet transfusion.

3.1.1.2 **Dose escalation after at least 3 months of treatment**

- Any other clinically important manifestation of LAL Deficiency on either clinical examination, laboratory assessment, or imaging which has either
 - not improved from baseline
 - improved and plateaued but has not normalized (Note: The definition of a plateauing of effect requires consideration of a minimal of

3 assessments.)

• failed to normalize within 12 months of initiation of treatment,

Manifestations include but are not restricted to the following: A decrease in weight for age defined as crossing \geq 2 major centile lines on standard weight for age curves, serum transaminases, albumin <3.5 g/dL, hepatomegaly, splenomegaly or lymphadenopathy.

If the subject continues to have criteria for dose escalation after at least 4 infusions at a dose of 3 mg/kg qw, the Investigator, may request of the Sponsor (in consultation with the SC) to increase the dose up to a maximum of 5 mg/kg qw on a case by case basis.

Prior to any dose change, serum lipid, serum liver, hematology, chemistry, ferritin and hs-CRP shall be obtained. Serum lipid and serum liver assessments should be taken 4, 8, and 12 weeks following any study drug or lipid drug dose change.

Figure 1Initial Dose Escalation- Safety Committee Review Flow

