- 2. Has no known additional measurements of hemoglobin that are below the age-adjusted LLN during the (minimum) 4-week period; and

Page 58 of 76

3. Had no transfusions during the (minimum) 4-week period, and also no transfusions for 2 weeks prior to the first hemoglobin measurement in the (minimum) 4-week period.

If all 3 criteria are met, the subject will be considered to have achieved TFHN on the date of the first hemoglobin assessment in the 4-week period. The proportion of subjects who achieve TFHN will be summarized and, if sufficient data are available, a summary of time to TFHN will be created.

A subject who is transfusion-free beginning at Week 6 will be considered to have maintained transfusion-free normal hemoglobin if, regardless of baseline hemoglobin value, the subject has no abnormally low hemoglobin values beginning at Week 8 of the study and continuing for at least 13 weeks (3 months). The proportion of subjects who have maintained transfusion-free normal hemoglobin will be summarized.

The Denver II total score and functional area scores will be derived from the questionnaire in accordance with the Technical Manual and compared to appropriate demographic norms. The total score and functional area scores will be summarized as continuous data and according to the classification as to whether the subject displays abnormal/normal development (Polat, 2010, *Pediatr Int*).

Shift tables will be used to tabulate dietary changes, including discontinuation of a low-fat/lowcholesterol diet and/or introduction of an unrestricted age-appropriate diet. Observed values and changes and/or percent changes from baseline in other exploratory efficacy endpoints will be tabulated for each evaluation timepoint.

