7.1.1 Handling of Missing Data

All data will be analyzed as they were collected in the database. Missing data will not be imputed.

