For anthropometric indicators of growth, age will be adjusted for prematurity if gestational age is <37 weeks and the subject is under 12 months of age. The adjustment will be made such that corrected age in months = chronological age in months minus the number of months premature.

Change and percent change from baseline in AST, ALT, and serum ferritin will be tabulated for each evaluation timepoint.

A subject will be considered to have achieved transfusion-free hemoglobin normalization (TFHN) if the subject meets all of the following criteria:

- 1. Has two post-baseline measurements of hemoglobin at least 4 weeks apart that are both above the age-adjusted lower limit of normal (LLN);
- 2. Has no known additional measurements of hemoglobin that are below the ageadjusted LLN during the (minimum) 4-week period; AND
- 3. Had no transfusions during the (minimum) 4-week period, and also no transfusions for 2 weeks prior to the first hemoglobin measurement in the (minimum) 4-week period.

If all 3 criteria are met, the subject will be considered to have achieved TFHN on the date of the first hemoglobin assessment in the 4-week period. The proportion of subjects who achieve TFHN will be summarized and, if sufficient data are available, a summary of time to TFHN will be created.

A subject who is transfusion-free beginning at Week 6 will be considered to have maintained transfusion-free normal hemoglobin if, regardless of baseline hemoglobin value, the subject has no abnormally low hemoglobin values beginning at Week 8 of the

study and continuing for at least 13 weeks (3 months). The proportion of subjects who have maintained transfusion-free normal hemoglobin will be summarized.

Denver II scores will be summarized with the number of patients who had the test done and tested 'normal', 'suspect', 'untestable' by visit for each of the categories. Additionally this data will be listed.

Shift tables may be used to tabulate dietary changes, including shift from low-cholesterol diet to unrestricted diet if sufficient data exist for summary.

Observed values and changes and percent changes from baseline in other exploratory efficacy endpoints will be tabulated for each evaluation time point. These will include changes in

- o alkaline phosphatase
- o gamma glutamyltransferase (GGT)
- o albumin
- o direct (conjugated), indirect (unconjugated), and total bilirubin levels;

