- o liver and spleen size/volume, as measured by ultrasound or magnetic resonance imaging (MRI). Liver and spleen volumes will be presented in statistical outputs as multiples of normal (where normal is defined as 2.5% of body weight for liver and 0.2% of body weight for spleen).
- hepatomegaly and/or splenomegaly (abdominal girth, liver size, and spleen size) by physical examination;
- o platelet counts;
- o serum lipid levels including
 - total cholesterol,
 - triglycerides,
 - high density lipoprotein (HDL),

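### Exploratory platelet change from baseline takes no account of recent platelet transfusion, at baseline or at follow-up

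*SAP*

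**What the plan says.** - **Platelets as an endpoint.** Protocol 3.2.2.1 and SAP 2.2.3 make platelet level an exploratory efficacy endpoint. SAP 9.1 states: "Observed values and changes and percent changes from baseline in other exploratory efficacy endpoints will be tabulated for each evaluation time point". The list that follows includes "platelet counts" and attaches no transfusion condition.
- **Baseline.** Protocol 8.1 takes the last value before the first infusion. For exploratory analyses it allows the first on-treatment value to stand in if there is no pretreatment one. Transfusion is not mentioned.
- **Platelet transfusion is foreseen.** Protocol 3.1.1.1 names "Ongoing requirement for blood and/or platelet transfusion" among the criteria for considering dose escalation.
- **Hemoglobin has transfusion rules.** For transfusion-free hemoglobin normalization (TFHN), SAP 9.1 asks that the infant "Has two post-baseline measurements of hemoglobin at least 4 weeks apart" above the lower limit of normal. It bars transfusion in that period "and also no transfusions for 2 weeks prior to the first hemoglobin measurement". Protocol 8.7 has the same rule. A second rule, for maintained normal hemoglobin, requires an infant to be free of transfusion from Week 6, with hemoglobin assessed from Week 8. Both rules concern post-baseline hemoglobin only.
- **Data handling.** SAP 7.1.1 says "All data will be analyzed as they were collected in the database", as does Protocol 8.13.
- **Records.** Protocol 4.5 has treatments and procedures recorded from consent onwards. SAP 8.3 summarizes prior therapies, and SAP 10.1.3 lists and tabulates concomitant ones. Nothing ties a transfusion to a platelet count.

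**The concern.** A platelet transfusion raises the count for a time whatever the study drug does. The plan deals with the parallel problem for hemoglobin but is silent for platelets, where the endpoint is the change itself. Followed as written, the platelet table mixes transfusion support with drug effect.

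Three features of the study make this harder to see through. There is no comparator (Protocol synopsis, Controls), so no other arm would show the artefact. The efficacy set is about 8 infants, so each one carries about an eighth of the mean. And the protocol expects infants to be hospitalized in the first weeks (Protocol 3.1), when laboratory visits are most frequent (Appendix A, Table 1) and transfusion support is most plausible.

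At stake is the reading of an exploratory result that also bears on the secondary objective about hematological parameters (Protocol 2.2). A reader of the table could not tell a drug response from a recent transfusion.

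**Working it through.** **1. Is there a planned figure to reproduce?** Not on this point. The documents give no platelet count, standard deviation, transfusion frequency or increment. The sample-size intervals in Protocol 8.2 and SAP 5 do reproduce by the Clopper-Pearson method: 6/8 gives (34.91%, 96.81%) and 1/18 gives (0.14%, 27.29%). They concern survival and do not depend on platelets.

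**2. Which values carry a transfusion condition?**

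| Value | Condition on recent transfusion | Place |
|---|---|---|
| Post-baseline hemoglobin, TFHN | None in the window of at least 4 weeks or the 2 weeks before it | Protocol 8.7, SAP 9.1 |
| Post-baseline hemoglobin, maintenance | Transfusion-free from Week 6, values from Week 8 | Protocol 8.7, SAP 9.1 |
| Baseline platelet count | None | Protocol 8.1 |
| Post-baseline platelet count | None | SAP 9.1 |

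**3. Shift in the mean change.** Inputs: n = 8 infants (Protocol 8.2, SAP 5), all with a baseline and a follow-up count. The rise r still present when the count is drawn is an assumption, taken as 20 to 100 x10^9/L and equal for all transfused values. Let f be the number of infants with a transfused follow-up count at the visit and b the number with a transfused baseline.

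Shift = (f − b) × r / n

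- f = 1, b = 0: 1 × 20 / 8 = 2.5 to 1 × 100 / 8 = 12.5 x10^9/L upwards.
- f = 2, b = 0: 2 × 20 / 8 = 5 to 2 × 100 / 8 = 25 x10^9/L upwards.
- f = 0, b = 1 or 2: the same amounts downwards. A transfused baseline affects every later visit, not just one.
- f = 1, b = 1 in different infants: the mean does not move, but two individual changes are wrong in opposite directions.

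**4. Effect on percent change in one infant.** Assume no drug effect and a true count T of 50 or 100 x10^9/L (again an assumption).

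- Transfused follow-up only, r / T: from 20 / 100 = +20% to 100 / 50 = +200%.
- Transfused baseline only, T / (T + r) − 1: from 100 / 120 − 1 = −17% to 50 / 150 − 1 = −67%.

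These ranges show sensitivity. They are not estimates for this trial.

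**The case against.** The case for leaving the plan alone has real weight.

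- Platelets are exploratory and Protocol 8.11.1 plans no formal tests. No survival conclusion depends on them. This stands and limits the importance of the point.
- The escalation criterion describes a contingency and gives no frequency. This stands: the size cannot be derived from the documents.
- SAP 7.1 also reports the median and quartiles, which one or two transfused values move much less than the mean. True, but a median does not show which values were affected, and with 8 infants several transfusions would move it too.
- The sentence about analyzing data as collected sits in the missing-data sections and is mainly about imputation. Fair. The gap rests on the absence of any platelet rule, not on that sentence.
- Protocol Section 8 provides for decisions on evaluability before database lock, all data are listed, and SAP 10.2 plots individual platelet counts. These give an opportunity to deal with transfused values but no rule for doing so. A reader would have to match listings by hand.

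A reader might also infer that hemoglobin normalization is biased: an anemic infant transfused just before baseline would look normal, leave the denominator and inflate the success rate. Only the protocol synopsis supports this, where the "proportion of subjects with abnormal hemoglobin at baseline who achieve transfusion-free hemoglobin normalization (TFHN) will be summarized". Protocol 8.7 and SAP 9.1 restrict TFHN to no baseline group. Protocol 8.1 takes treated subjects as the denominator, and SAP 7.1 by default takes all subjects in the analysis population. If 4 of 8 infants achieved TFHN, the SAP would report 4/8 = 50% whatever their baseline values. What is left is a mismatch of wording between synopsis and body.

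**Conclusion.** The gap is real and modest. Platelet change and percent change are tabulated without regard to recent platelet transfusion at either end of the comparison, in an uncontrolled study of about 8 infants that itself foresees such transfusions. Under an assumed rise of 20 to 100 x10^9/L and 8 evaluable infants, one transfused value moves the mean change by 2.5 to 12.5 x10^9/L and two by 5 to 25, in either direction.

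Two stronger readings go beyond the documents. One is that the platelet result will in fact reflect transfusion, or will favor the drug: frequency and increment are not given, and a transfused baseline works against the drug. The other is that transfused counts must be removed from the main table. The hemoglobin rule defines one responder endpoint and does not declare every recently transfused count unusable. Exclusion would also lose an infant with a transfused baseline from the change columns at every visit unless another baseline is used, and would tend to remove the sicker infants.

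**What to change.** In SAP 9.1, for platelet count:

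1. Keep the as-collected table of observed value, change and percent change.
2. Flag every count, baseline and follow-up, taken within a pre-specified window after a platelet transfusion. Two weeks is the plan's own precedent, but it was set for hemoglobin. Either adopt it openly or justify a platelet-specific window.
3. Show the number of infants with a flagged value at each visit, and mark flagged points on the platelet plots.
4. Add a supplementary table that omits flagged values.
5. State how a flagged baseline is handled in that table. Appendix A, Table 1 schedules clinical laboratory tests at Screening and before the Week 0 dose. One option is therefore to use the latest unflagged pretreatment count and, if there is none, to keep the infant in the observed-value columns only. Say whether the on-treatment substitute baseline in Protocol 8.1 may be used here.

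Separately, align the synopsis denominator for TFHN with Protocol 8.7 and SAP 9.1.

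The cost is SAP wording, one derived flag and one more table. Platelet count belongs to the mandatory laboratory tier (Protocol 5.1.11), and TFHN already needs transfusion dates. One check is needed: Protocol 4.5 records treatments from consent, so a window before the baseline count may reach back further and rely on dated prior-therapy records. The supplementary table will have fewer evaluable values, and the loss will fall more on sicker infants, which is why it should accompany the main table and not replace it.

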10.1 Adverse Events

This SAP specifies standard tabular summaries for adverse events. If the number of any particular type of event is small, the data may be presented in listing format, rather than as a tabular summary.

All AEs will be coded using the MedDRA for the study (version 9.1 or higher).

The severity of AEs will be graded on a 5 point scale according to National Cancer Institute (NCI) Common Terminology Criteria for Adverse Events (CTCAE), version 4.0 or higher.

For the purpose of this study, an IRR will be defined as any AE that occurs during the 2-hour IMP infusion or within 4 hours after the IMP infusion and is assessed by the Investigator as at least possibly related to IMP.

TEAEs are defined as AEs occurring or worsening with an onset at the time of or following the start of treatment with study medication and up to 30 days after the last dose of SBC-102 (completion of the follow-up visit).

Attempts will be made to resolve any missing or partial AE dates with the site; however, if these cannot be resolved, to handle the missing or partial AE start/end date, the following rules will be implemented:

If the start date and time of an AE are partially or completely missing, the AE will be assumed to be treatment-emergent if it cannot be definitely shown that the AE did not occur or worsen during the treatment emergent period (worst case approach). Missing dates and times will not be imputed, but will be shown on listings as incomplete.

Thus, the following approach will be taken:

- If the start time of an AE is missing, but the start date is complete, an AE will only be excluded from treatment-emergent AEs if the start day is before day of first treatment or the start day is after end day of the treatment-emergent period.
- If the start time and day are missing but the start month is complete, an AE will only be excluded from treatment emergent AEs if the start month is before month of first treatment or the start month is after end month of treatment-emergent period or if the stop date/time is before the start of first treatment.
- If the start day and month are missing but the start year is complete, an AE will only be excluded from treatment-emergent AEs if the start year is before year of first treatment or if the start year is after end year of treatment-emergent period or if the stop date/time is before the start of first treatment.
- If the start date is completely missing, an AE will not be excluded from treatmentemergent AEs unless the stop date/time is before the start of first treatment.

An Overall AE summary table will be presented and will include the number of subjects with:

- All treatment-emergent AEs
- IRRs
- SAEs
- Treatment-emergent AEs related to SBC-102
- Treatment-emergent AEs leading to discontinuation from the study

Summaries of number of events and incidence rates (frequencies and percentages of subjects) of AEs by MedDRA SOC and Preferred Term will be prepared. Such summaries will also be displayed for all AEs by intensity and by relationship to study drug.

Each subject will be counted only once within each level of the summary. If a subject experiences more than one AE within a level, only the AE with the strongest relationship or the maximum intensity, as appropriate, will be included in the summaries of relationship and intensity.

No inferential statistical tests will be performed.

In addition, frequency of AEs, SAEs, and IRRs will be presented for time periods spanning the entire course of treatment with SBC-102: from the start of dosing with SBC-102 in this study to 3 months after the first dose, >3 to 6 months, >6 to 12 months, >12 to 18 months, >18 to 24 months and >24 months.

All AEs will be listed. Separate listings of SAEs, IRRs, AEs leading to study discontinuation, and AEs leading to discontinuation of SBC-102 will also be provided.

As appropriate, a summary of numbers of events and incidence rates (frequencies and percentages or subjects) of IRRs, and AEs leading to withdrawal from the study by SOC and Preferred Term will be prepared for the FAS. No inferential statistical tests will be performed.

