6.5 Infusion Associated Reactions

Infusion-associated reactions will be considered AEs of special interest. Any AE that occurs during the infusion or within 4 hours after the IMP infusion is completed and is assessed by the Investigator as at least possibly related to IMP will be designated as an IAR. In addition, if, at any time during the study, the Investigator observes symptoms that he/she considers to be consistent with an IAR or hypersensitivity reaction related to administration of study drug, the symptoms should be recorded as an AE(s) and designated as an IAR(s). Individual adverse event terms should be recorded rather than the terms, IAR or Infusion Associated Reaction.

As with any ERT, medications and equipment for the treatment of hypersensitivity reactions must be available for immediate use in case of unexpected, severe hypersensitivity reactions. These supplies include, but are not limited to, oxygen, acetaminophen, antihistamines (e.g., diphenhydramine, parenteral and oral [PO]), corticosteroids, epinephrine and cardiopulmonary resuscitation devices.

General guidelines for classifying the severity of a reaction are provided in Section 7.1.1.

For similar biological products, most acute IARs occur within 2 hours of the infusion. Signs of a possible acute IAR may include:

• Hyperemia (flushing), fever and/or chills, nausea, pruritus, urticaria, gastro-intestinal symptoms (vomiting, diarrhea, abdominal cramping) cardiopulmonary reactions, including chest pain, dyspnea, wheezing, stridor, hypotension or hypertension.

If any of the above signs and symptoms are observed during the infusion and the subject remains hemodynamically stable:

- The infusion rate must be slowed by 50% (reduced to half the rate being given at the onset of the event, e.g. from 10 mL/hr to 5 mL/hr) and the infusion time extended in accordance with the institutional standard of care. The infusion rate may be decreased further by 25% if symptoms persist. If the event resolves, the infusion should continue for a minimum of 30 minutes at the reduced rate before the rate is increased to 75% of the original rate on the infusion schedule. If the subject tolerates infusion at 75% of the original rate for at least 30 minutes the original rate may be restored for the remainder of the infusion.
- In accordance with institutional standard of care for subject's age, treatment with oral anti-pyretic and/or antihistamine should be considered.

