7.3 Recording of Adverse Events

At each contact with the subject (and the subject's parent or legal guardian), the Investigator must seek information on AEs by specific questioning and, as appropriate, by examination. Information on all AEs should be recorded immediately in the source documentation, and in the eCRF. All clearly related signs, symptoms, and abnormal diagnostic procedures results should be recorded under one diagnosis.

AEs will be recorded from the time of signing of the informed consent until completion of the last scheduled visit, i.e., the follow-up visit. AEs occurring after signing the informed consent but prior to the first dose of study medication will only be recorded if assessed as related to protocol procedures or requirements. Any AEs remaining unresolved at the completion of the last scheduled visit should be recorded as ongoing. Ongoing AEs/SAEs should continue to be followed up for the period specified in Section 7.2.2 but without further recording in the eCRF. However, follow-up information on SAEs must be reported to the Sponsor or designee as described in Section 7.4.1. Any SAE that occurs after the study period and is considered to be related to the study treatment or study participation should be recorded and reported immediately.

Any AE that occurs within 24 hours of the infusion will be recorded by time and date, AEs occurring 24 hours after the infusion will be recorded by date only. The date and time, or the date when the AE started and stopped, as well as the intensity, seriousness, action taken with regard to the study treatment, causality assessment and outcome of the event will be recorded for each AE.

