7.4.1 Investigator Reporting: Notifying the Study Sponsor

Any SAE, IAR or unanticipated problem posing risk of harm to subjects, must be reported to the Sponsor, or designee immediately, and no later than 24 hours of the Investigator's first knowledge of the event. To report such events, a SAE/IAR form must be completed by the Investigator and sent to the study Sponsor or designee within 24 hours. The Investigator will keep a copy of this SAE or IAR form on file at the study site.

The Investigator must promptly provide further information on the SAE, IAR, or the unanticipated problem. This should include a copy of the completed SAE or IAR form, and any other diagnostic information that will assist the understanding of the event. Significant new information on ongoing SAEs or IARs must be reported to the Sponsor or designee immediately and no later than 24 hours of the Investigator's knowledge.

Report SAEs and IARs by phone, fax or email to:

For cases in North America	For cases in Europe							
Phone: PPD	Fax: PPD							
Fax:	Email: ^{PPD}							
Email ^{PPD}								

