Appendix C: Dose Modification and Stopping Rules for LAL-CL03 Study

In the absence of an approved grading scale that can be applied to specific patient populations, this protocol will apply the National Cancer Institute Common Toxicity Classification of Adverse Events (NCI CTCAE), version 4.0 or higher. (http://evs.nci.nih.gov/ftp1/CTCAE/CTCAE_4.03_2010-06-14_QuickReference_8.5x11.pdf).

The following stopping rules apply to the decision to pause dosing in individual subjects:

For IARs (refer to the definition in Section 6.5), the following stopping rules will apply:

 Subjects who develop a Grade 3 (severe) or higher IAR must stop treatment until their information is reviewed by the SC. Dosing with alterations to the infusion regimen (e.g., pretreatment and/or slowing the rate of infusion) may resume once the SC and the Sponsor approve. Confirmation may also be sought from regulatory authorities prior to resuming dosing.

Page 76 of 76

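### The SAP counts only timed infusion reactions and summarises only vital-sign maxima; neither is reconciled with protocol sections 6.5 and 8.8.3

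*SAP*

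**What the plan says.** The SAP calls these events IRRs and the protocol calls them IARs.

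**Infusion reactions.** SAP section 10.1: "an IRR will be defined as any AE that occurs during the 2-hour IMP infusion or within 4 hours after the IMP infusion", with the further condition that the Investigator rates the event at least possibly related. Protocol section 6.5 has that timed route, without a fixed infusion length, and then a second one: "if, at any time during the study, the Investigator observes symptoms that he/she considers to be consistent with an IAR or hypersensitivity reaction" related to study drug, the symptoms are recorded as AEs and designated IARs. The same section adds: "Individual adverse event terms should be recorded rather than the terms, IAR or Infusion Associated Reaction". Appendix C of the protocol ties its rule to this wider definition: "For IARs (refer to the definition in Section 6.5), the following stopping rules will apply".

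The SAP definition feeds the overall AE table, the by-period frequencies, the summary by system organ class and preferred term, and a listing: "Separate listings of SAEs, IRRs, AEs leading to study discontinuation, and AEs leading to discontinuation of SBC-102 will also be provided". (The SAP's summary of amendments replaces the period cut-points given in section 10.1, but not the definition of the event counted.)

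**Vital signs.** Protocol section 8.8.3 summarises the change from the pre-infusion value to every time point during and after the infusion. SAP section 10.3 summarises, within each infusion, the maximum result and the maximum change from pre-infusion, and lists all readings by subject. It specifies no minimum and does not say whether the change is signed or absolute.

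**The concern.** IARs are the protocol's adverse events of special interest, and their incidence is a safety endpoint in both documents (protocol section 3.2.2.2, SAP section 2.3). If the SAP is programmed as written, the reported incidence refers to a narrower event than the one the Investigator designates and sends to the Sponsor. Incidence could then be understated in a study of about 10 subjects, where one subject matters.

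The vital-sign summary looks mainly in one direction. Protocol section 6.5 describes hypotension as a decline approaching 20-30% of the pre-infusion value, so a fall is part of the signal the summary should show. A summary built on maxima can miss it.

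**Working it through.** No figure in the plan needs reproducing. The check compares the texts and then sizes the effect on assumed values.

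**1. Which events each definition counts**

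| Event | Protocol 6.5 | SAP 10.1 |
|---|---|---|
| Related AE during infusion or up to 4 h after | IAR | IRR |
| Onset after 4 h, Investigator designates it an IAR | IAR | not an IRR |

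The second row is absent from the IRR count, the by-period frequencies, the IRR summary by class and term, and the IRR listing. It stays in the treatment-emergent AE outputs, the related-AE outputs if so assessed, the SAE outputs if serious, and the listing of all AEs. A reader could not recognise it there by its term, because individual terms are recorded. Protocol section 7.3 names no IAR designation among the attributes kept ("action taken with regard to the study treatment, causality assessment and outcome of the event will be recorded for each AE"). Protocol section 7.4.1 does provide another source: "a SAE/IAR form must be completed by the Investigator".

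A minor point: the SAP's 2-hour infusion is not a duration in the supplied protocol, whose section 6.4.2 sets the rate by weight.

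**2. Size for IRR incidence**

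Shift in incidence = 1/n for one subject whose only IAR is late.
- n = 8: 1/8 = 12.5 points.
- n = 10: 1/10 = 10.0 points.
- If that subject also has an in-window IRR: 0 points.

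The documents do not give the frequency of late IARs.

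**3. Vital signs, illustrative systolic values (mmHg), pre-infusion 90**

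The protocol's 20-30% decline is 0.20 × 90 = 18 (reading 72) to 0.30 × 90 = 27 (reading 63).

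| Later readings | Changes | Maximum result | Maximum change, signed | Maximum change, absolute |
|---|---|---|---|---|
| 95, 63 | +5, −27 | 95 | +5 (fall hidden) | −27 (fall shown) |
| 120, 63 | +30, −27 | 120 | +30 (fall hidden) | +30 (fall hidden) |

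Defining the sign therefore settles the first case but not the second.

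On the initial schedule of protocol section 5.1.9 (every 15 minutes during the infusion, every 30 minutes from 0 to 4 hours after, with the end-of-infusion reading shared), an assumed 2-hour infusion gives 8 + 9 − 1 = 16 readings per vital sign. An assumed 1-hour infusion gives 4 + 9 − 1 = 12, and a 3-hour infusion 12 + 9 − 1 = 20. The SAP reduces each set to one maximum and one maximum change.

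**4. Is either difference declared?**

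SAP section 13 lists one change from the protocol, on the Denver II total score. The SAP's summary of amendments covers urinalysis and ADA outputs, spaghetti plots, the per-protocol set, AE periods and Denver II. Neither mentions the IRR definition or vital signs.

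**5. Which protocol version?**

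SAP section 1 cites Amendment 10 of 24 January 2014. The supplied protocol carries the date 05 January 2016 in Appendix A. The two differ elsewhere too: treatment is for up to 4 years in SAP section 3.1 and up to 5 years in protocol section 3.1. Amendment 10 is not supplied, so the origin of the mismatch cannot be traced.

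**The case against.** The strongest reply is that the comparison uses the wrong protocol version. The SAP's design sections state that they are copied from the protocol, and they use older terms (infusion related reaction, seroconversion, suboptimal response). The narrower definition may simply reproduce Amendment 10. This stands as a limit on what can be claimed: the texts show an unreconciled difference and do not show that the SAP departed from the version it was written to. It does not remove the need to act, because the final analyses in protocol section 8 cover the whole treatment period.

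Second, the effect may be nil. Protocol section 6.5 notes that for similar products most acute reactions occur within 2 hours, and a late reaction would still be visible in the AE listing of a study this small. This also stands as a limit on size. The endpoint, though, is IAR incidence, and the general AE outputs do not report it.

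Third, Appendix C is applied during the trial under protocol section 6.5, so the SAP definition does not affect subject protection. That is right; the point concerns reporting only. It is also fair that the eCRF, which is not supplied, may hold an IAR flag that section 7.3 does not list.

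Fourth, on vital signs, maximum change may mean the largest absolute change, the table shells are in an addendum that is not supplied, and all readings are listed. A fall assessed as a related reaction within the window also enters the AE and IRR outputs. Full by-timepoint tables would be long. With weekly dosing to week 96 and every other week to week 260, there are about 96 + (260 − 96)/2 = 178 infusions. At the lightest monitoring, with assumed 2-hour infusions, there are 4 + 5 − 1 = 8 readings each, so 178 × 8 = 1,424 rows per vital sign. Condensing within infusion is therefore reasonable. Condensing to maxima alone is not, because the 120/63 example hides a 30% fall under either reading of the term. That example is constructed, and the documents do not say how often such a pattern would occur.

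**Conclusion.** The concern holds as an unreconciled difference between the SAP and the supplied protocol. Applied literally, SAP section 10.1 gives a narrower count of the protocol's adverse event of special interest, and SAP section 10.3 gives a summary that can omit a fall in blood pressure.

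The incidence effect is 10 to 12.5 points for each subject whose only IAR is late, and zero if there is none. The vital-sign effect is shown on assumed readings only and depends partly on an undefined term that the unsupplied addendum may settle. The primary survival endpoint is not affected. The changes should be made, but the trial's main conclusion does not depend on them. Confidence is medium, because Amendment 10, the addendum and the eCRF are not available.

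**What to change.** - **SAP section 10.1:** define an IRR as every AE designated an IAR under either route of protocol section 6.5, and refer to the actual infusion instead of a 2-hour one. If the designation is not in the analysis database, match AE records to the SAE/IAR forms. Splitting IRRs by onset within 4 hours or later is optional.
- **SAP section 10.3:** for each vital sign, add the minimum value and both the largest decrease and the largest increase from pre-infusion. Alternatively, restore the by-timepoint changes of protocol section 8.8.3.
- **SAP section 13:** update the SAP to the current protocol and list any difference that is kept on purpose.

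The cost is SAP wording, minor programming and some reconciliation of forms with AE records. Vital signs are already collected under protocol section 5.1.9. AE onset is collected under section 7.3, with clock time for events within 24 hours of the infusion. The reported IRR incidence may come out higher.
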